6.5.3.4. Dose Delays

Applicable to PF-05082566 and rituximab.

Dose Delay is the difference between the actual time between two consecutive non-zero doses and the planned time between the same two consecutive non-zero doses.

PF-05082566 in Portion A

Dose delay in Cycle x (days) = Date of first dose of PF-05082566 in Cycle x – Date of first dose of PF-05082566 in Cycle (x-1) – 28, where $x > 1$.

PF-05082566 in Portion B

In Cycle 1,

Dose delay (days) = Study day of first dose of PF-05082566 – 9 [Note: Cycle 1 starts on Day -7 and the first dose of PF-05082566 is scheduled for Cycle 1 Day 1].

In Cycle x,

Dose delay in Cycle x (days) = Date of first dose of PF-05082566 in Cycle x – Date of first dose of PF-05082566 in Cycle (x-1) – 28, where $x > 1$.

Rituximab

Dose delay for Dose x (days) = Date of Dose x – Date of Dose (x-1) – 7, where $x > 1$.

Dose delays will be grouped into the following categories:

- No delay.
- 1-2 days delay.
- 3-6 days delay.
- 7 or more days delay.

For example, for PF-05082566, administered on a 4-week schedule, if one patient receives PF-05082566 on Day 1, then the next PF-05082566 administration date will be on Day 29; however, if the patient receives PF-05082566 at Day 30 or 31, this will be summarized in the 1-2 days delay category.

The number and percentage of patients with delayed study drug administration and maximum length of delay, ie, the worst case of delay if patients have multiple dose delays will be summarized.

6.5.3.5. Infusion Rate Reductions

Applicable to PF-05082566 and rituximab.

The number and percentage of patients with at least one infusion rate reduction of $\geq 50\%$ compared to the first infusion rate reported in the CRF (first entry on the first dosing record page) as well as the frequency of patients with 1, 2, 3 or ≥ 4 infusion rate reductions of $\geq 50\%$ will be summarized.

6.5.3.6. Infusion Interruptions

An infusion interruption is defined as an infusion that is stopped and re-started on the same day (ie, for a visit more than one infusion start time and infusion end time are recorded).

The number and percentage of patients with at least one infusion interruption as well as the frequency of patients with 1, 2, 3, or ≥ 4 infusion interruptions will be summarized.

6.5.4. Concomitant Medications and Non-drug Treatments

The following analyses will be based on the safety analysis set by treatment group.

Concomitant medications are medications, other than study medications, which started prior to first dose date of study treatment and continued on on-treatment period as well as those started during the on-treatment period. **Prior medications** are medications, other than study medications and pre-medications for study drug, which are started before the first dose of study treatment.

Prior and concomitant medications will be summarized from the ‘Prior and Concomitant Drug/Non-Drug Treatment’ eCRF page.

Summary of prior and concomitant medications will include the number and percentage of patients by Anatomical Therapeutic Chemical (ATC) Classification level 2 and preferred term. A patient will be counted only once within a given drug class and within a given drug name, even if he/she received the same medication at different times. If any prior or concomitant medication is classified into multiple ATC classes, the medication will be summarized separately under each of these ATC classes. The summary tables will be sorted on decreasing frequency of drug class and decreasing frequency of drug name in a given drug class. In case of equal frequency regarding drug class (respectively drug name), alphabetical order will be used. In case any specific medication does not have ATC classification level 2 coded term, it will be summarized under ‘Unavailable ATC classification’ category.

A listing of concomitant medications will be created with the relevant information collected on the ‘Prior and Concomitant Drug Treatment’ eCRF page.

All concurrent procedures, which were undertaken any time during the on-treatment period, will be listed according to the eCRF page ‘Prior and Concomitant Non-Drug Treatment’.

A listing of concurrent procedures will be created with the relevant information collected on the ‘Prior and Concomitant Non-Drug Treatment’ eCRF page.

6.5.5. Subsequent Anti-cancer Therapies

The following analyses will be based on the FAS by treatment group.

Anti-cancer treatment will be provided in a data listing with data retrieved from ‘Follow-up Systemic Therapy’, ‘Concomitant Radiation Therapy’ and ‘Concomitant Surgery’ eCRF pages.

Number and percentage of patients with any anti-cancer therapy after discontinuation will be tabulated overall and by type of therapy based on the data collected from the ‘Follow-up anti-cancer Therapy’ eCRF page.

6.6. Safety Summaries and Analyses

The Safety Analysis Set will be the primary population for safety evaluations. Summaries of AEs and other safety parameters will be based on the safety analysis set by treatment group.

All summaries of related AEs (PF-05082566 plus rituximab) will further be presented as PF-05082566-related, rituximab -related, or related to both study treatments.

All summaries described below by SOC and PT will further be presented by PT in decreasing frequency based on the frequencies observed in all treatment groups combined.

6.6.1. Adverse Events

Treatment-emergent adverse events (TEAEs) are those events with onset dates occurring during the on-treatment period for the first time, or if the worsening of an event occurs during the on-treatment period as defined in [Section 3.8.1](#).

All analyses described will be based on TEAEs (started during the on-treatment period) if not otherwise specified. The AE listings will include all AEs (whether treatment-emergent or not). AEs outside the on-treatment period will be flagged in the listings.

- **Related Adverse Events:** adverse events with relationship to study treatment (as recorded on the AE eCRF page, Relationship with study treatment = Related) reported by the investigator and those of unknown relationship (ie, no answer to the question ‘Relationship with study treatment’).
- **Serious Adverse Events (SAE):** serious adverse events (as recorded on the AE eCRF page, Serious Adverse Event = Yes).
- **Adverse Events Leading to Permanent Treatment Discontinuation:** adverse events leading to permanent discontinuation of study treatment (as recorded on the AE eCRF page, Action taken with study treatment = Drug withdrawn).
- **Adverse Events Leading to Death:** adverse event leading to death (as recorded on the AE eCRF page, Outcome = Fatal, as well as AEs of Grade 5).

Unless otherwise specified, AEs will be summarized by number and percentage of patients with the AE in the category of interest as described above, by treatment group, primary SOC and PT in decreasing frequency observed in all treatment groups combined.

Each patient will be counted only once within each SOC or PT. If a patient experiences more than one AE within a SOC or PT for the same summary period, only the AE with the strongest relationship or the worst severity, as appropriate, will be included in the summaries of relationship and severity.

6.6.1.1. All Adverse Events

Adverse events will be summarized by worst severity (according to NCI-CTCAE version 4.03) per patient, using the latest version of MedDRA preferred term (PT) as event category and MedDRA primary system organ class (SOC) body term as Body System category.

In case a patient has events with missing and non-missing grades, the maximum of the non-missing grades will be displayed. No imputation of missing grades will be performed.

The following tables will be created:

- The overall summary of AEs table will include the frequency (number and percentage) of patients with each of the following by treatment group:
 - TEAEs.

- TEAEs, Grade ≥ 3 .
- Related TEAEs.
- Related TEAEs, Grade ≥ 3 .
- TEAEs leading to permanent treatment discontinuation.
- Related TEAEs leading to permanent treatment discontinuation.
- Serious TEAEs.
- Related Serious TEAEs.
- TEAEs leading to death.
- Related TEAEs leading to death.
- TEAEs by SOC and PT and worst grade.
- Related TEAEs by SOC and PT and worst grade.
- TEAEs leading to death by SOC and PT.
- Related TEAEs leading to death by SOC and PT.
- TEAEs by SOC and PT: displaying in separate columns the All TEAEs / Related TEAEs / Grade ≥ 3 TEAEs / Related Grade ≥ 3 TEAEs.
- TEAEs Excluding SAEs, with frequency $\geq 5\%$ in any treatment group by SOC and PT.

6.6.1.2. Adverse Events Leading to Treatment Discontinuation

The frequency (number and percentage) of patients with each of the following will be presented for TEAEs leading to permanent discontinuation of each study drug and study treatment, by treatment group:

- TEAEs leading to discontinuation of PF-05082566 by SOC and PT;
- Related TEAEs leading to discontinuation of PF-05082566 by SOC and PT;
- TEAEs leading to discontinuation of rituximab by SOC and PT;
- Related TEAEs leading to discontinuation of rituximab by SOC and PT;
- TEAEs leading to permanent discontinuation of study treatment;
- Related TEAEs leading to permanent discontinuation of study treatment.

The listing of all AEs leading to treatment discontinuation will also be provided with the relevant information.

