5. STUDY TREATMENTS

For the purposes of this study, and per International Conference on Harmonisation (ICH) guidelines, investigational product is defined as a pharmaceutical form of an active ingredient or placebo being tested or used as a reference/comparator in a clinical trial, including a product with a marketing authorization when used or assembled (formulated or packaged) in a way different from the approved form, or when used for an unapproved indication, or when used to gain further information about an approved use (ICH E6 1.33).

For this study, the investigational products is PF-05082566. Rituximab is considered to be an investigational product in some countries and not others, according to local regulations.

Portion A:

During the dose escalation phase, PF-05082566 will be administered in escalating doses with available dose levels including the following: 0.006, 0.03, 0.06, 0.12, 0.18, 0.24, 0.30 (using the 3+3 design), and 0.6, 1.2, 2.4, 5.0 and 10 mg/kg (using the TITE-CRM design) by IV infusion of 1 hour (-5/+15 min) every 4 weeks. If a dose reduction is needed for patients being treated with 0.6 to 10 mg/kg, a dose reduction may be made from the next highest planned dose level to one of the following specific dose levels: 0.45, 0.9, 1.8, and 3.6 mg/kg. If the 10 mg/kg dose is not well tolerated, there is an option to de-escalate to 7.5 mg/kg. Each patient will initially receive the first dose on Cycle 1 Day 1 with a 28-day observation period. Cycle 2 will start on Day 29.

In the expansion cohort, PF-05082566 will be administered at either 0.24 mg/kg, 0.6 mg/kg, or 1.2 mg/kg by IV infusion of 1 hour (-5/+15 min) every 4 weeks. If a dose reduction is required due to the treatment-related toxicity, this may be allowed as an alternative to discontinuation of treatment. No dose reduction is allowed for patients treated at the 0.24 mg/kg dose level. See [Section 5.4.4](#) for details.

Japan cohort(s) in Portion A:

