5.4.4. Dose Modifications for PF-05082566

Following dosing interruption or cycle delay due to toxicity (see [Section 5.4.2](#) and 5.4.3), the PF-05082566 dose may need to be reduced when treatment is resumed.

No specific dose adjustments are recommended for Grade 1/2 treatment-related toxicity. However, investigators should always manage their patients according to their medical judgment based on the particular clinical circumstances.

Patients experiencing recurrent and intolerable Grade 2 toxicity may resume dosing at the next lower dose level, if possible, once recovery to Grade ≤ 1 or baseline is achieved.

Patients experiencing an AE meeting the DLT definition (see [Section 3.4](#) for DLT definition) may resume dosing at the next lower dose level, if possible, once adequate recovery is achieved (see [Section 5.4.3](#)).

Dose reduction of PF-05082566 by 1 and, if needed, 2 dose levels (Table 11) will be allowed depending on the type and severity of toxicity encountered. Patients requiring more than 2 dose reductions will be permanently discontinued from the study treatment and entered into the follow-up phase. Once a patient has a dose reduction of PF-05082566 for a PF-05082566 related toxicity, the dose will not be re-escalated. All dose modifications and adjustments must be clearly documented in the patient's source notes and CRF.

Patients treated with PF-05082566 at 0.24 mg/kg requiring a dose reduction should be permanently withdrawn from study treatment.

Table 11. Available Dose Levels for PF-05082566 (mg/kg)

1.2
0.6
0.24

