6.5.3.3. Dose Reductions

Applicable to PF-05082566 and rituximab.

Dose reduction is defined as actual non-zero dose < 90% of the planned dose.

The number and percentage of patients with at least one dose reduction as well as a breakdown of the number of dose reductions (1, 2, 3, ≥ 4) will be summarized.

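### The by-dose tables of adverse events leading to discontinuation are biased upward at 0.24 mg/kg, because only that expansion dose has no reduction step and no planned table counts reductions and discontinuations together

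*SAP*

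**What the plan says.** Protocol 5.4.4 sets the reduction rule for the expansion doses, on a ladder of 1.2, 0.6 and 0.24 mg/kg (Table 11):

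- In general: "Dose reduction of PF-05082566 by 1 and, if needed, 2 dose levels (Table 11) will be allowed".
- At the lowest dose: "Patients treated with PF-05082566 at 0.24 mg/kg requiring a dose reduction should be permanently withdrawn from study treatment". Protocol 5 repeats this for Portions A and B: "No dose reduction is allowed for patients treated at the 0.24 mg/kg dose level".
- A patient with an event meeting the DLT definition "may resume dosing at the next lower dose level, if possible, once adequate recovery is achieved". Recurrent, intolerable Grade 2 toxicity is the second trigger in the same section.

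The SAP then handles the consequences in separate places:

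- SAP 6.6.1 defines the discontinuation category as "adverse events leading to permanent discontinuation of study treatment (as recorded on the AE eCRF page, Action taken with study treatment = Drug withdrawn".
- SAP 6.6.1.1 and 6.6.1.2 tabulate it by treatment group, which SAP 3.7.1 defines by dose (with or without rituximab). The first table listed in SAP 6.6.1.2 is "TEAEs leading to discontinuation of PF-05082566 by SOC and PT". Under SAP 4.2 a randomised patient stays under the assigned dose after a reduction.
- SAP 6.5.3.3 summarises "The number and percentage of patients with at least one dose reduction as well as a breakdown of the number of dose reductions". A reduction there is any non-zero dose below 90% of plan, with no link to adverse events.

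No table in SAP 6.6.1.1 or 6.6.1.2 counts TEAEs leading to dose reduction, or to reduction and discontinuation combined. Neither section comments on the unequal options for reduction.

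**The concern.** The same toxicity enters the discontinuation table at 0.24 mg/kg, but on first occurrence it can be handled outside that table at 0.6 and 1.2 mg/kg. Part of any difference between doses then reflects the handling rule and not the drug. The dose-reduction table does not repair this. A protocol-directed step down cannot occur at 0.24 mg/kg, so that table leans the opposite way, and its counts are not tied to adverse events.

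The direction matters because Protocol 3.3.1 says the Portion A expansion cohorts, including the randomised melanoma patients, are to support selection of the RP2D with safety, tolerability, PK and preliminary efficacy data. Portion B has the same asymmetry. FL-1 (1.2 mg/kg) and, if enrolled, FL-2 (0.24 mg/kg) inform the FL-3 dose partly on tolerability (Protocol 3.1.2). Discontinuation for adverse events is a summary that readers naturally compare across doses.

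**Working it through.** The documents give no figure on this point, so there is none to reproduce. The calculation below is illustrative.

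**Inputs from the documents.** Reduction steps available: 0 at 0.24 mg/kg, 1 at 0.6, 2 at 1.2 (Protocol 5.4.4, Table 11). About 40 patients randomised 2:1:1 to 0.6, 0.24 and 1.2 mg/kg (Protocol 5.1.1 and 3.1.1), so 20/10/10. Target of about 20 melanoma patients per dose (SAP 5.1.1). No DLTs in 133 patients, 86 of them in Portion A (Protocol 1.4).

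**Assumed inputs.** d is the chance of discontinuing for an adverse event by a route common to all doses, such as no recovery after 8 weeks of delay (Protocol 5.4.3). q is the chance of a first toxicity that needs a reduction. s is the chance of a further one after a reduction.

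**Formulas.** Expected proportion in the discontinuation table:

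- 0.24 mg/kg: d + q
- 0.6 mg/kg: d + q·s
- 1.2 mg/kg: d + q·s²

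With d, q and s equal across doses, the artificial excess at 0.24 mg/kg is q(1 − s) over 0.6 mg/kg and q(1 − s²) over 1.2 mg/kg. It does not depend on d.

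**Equal true toxicity, d = 5%, s = 25%:**

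| q | 0.24 | 0.6 | 1.2 | Excess over 0.6 | Excess over 1.2 |
|---|---|---|---|---|---|
| 2% | 5 + 2 = 7.0% | 5 + 0.5 = 5.5% | 5 + 0.125 = 5.1% | 1.5 points | 1.9 points |
| 10% | 5 + 10 = 15.0% | 5 + 2.5 = 7.5% | 5 + 0.625 = 5.6% | 7.5 points | 9.4 points |

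Exact binomial enumeration with 20 patients per dose gives the chance that 0.24 mg/kg shows strictly the highest proportion: 31% for q = 2% and 61% for q = 10%. With 10/20/10 at 0.24/0.6/1.2 mg/kg it is 29% and 52%. If reductions and discontinuations are counted together, every dose has expected proportion d + q, and with 20 per dose the chance is 23% and 26%.

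**Toxicity rising with dose, q = 2/5/10% at 0.24/0.6/1.2 mg/kg:**

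- d = 5% at all doses, s = 25%: 7.0/6.3/5.6%. The true order is reversed.
- d = 5% at all doses, s = 50%: 7.0/7.5/7.5%. The lowest dose is lowest.
- d = 2/5/10%, s = 25%: 4.0/6.3/10.6%. The lowest dose is lowest.

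With equal d, 0.24 mg/kg exceeds 0.6 mg/kg only if q at 0.24 is greater than s times q at 0.6.

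**How large q could be.** For 0 DLTs in n patients the one-sided 95% upper bound is 1 − 0.05^(1/n): 2.2% for n = 133 and 3.4% for n = 86. In 20 patients at 0.24 mg/kg these bounds correspond to 20 × 0.0223 ≈ 0.45 and 20 × 0.0342 ≈ 0.68 DLT-driven withdrawals. They cover the DLT trigger only, within its two-cycle window. The documents give no rate for recurrent, intolerable Grade 2 toxicity.

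**The case against.** A reader might infer that 0.24 mg/kg is bound to look least tolerable. The documents do not support that. Some discontinuation routes are common to all doses (Protocol 5.4, 5.4.3, 7.1.5), the order depends on true toxicity and recurrence, and chance is large with 10 to 20 patients per dose. Leaving out the common routes would also overstate the ratios between doses.

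Other points on that side:

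- Conversion is not automatic. Protocol 5.4.4 is permissive about resuming at a lower level, and Protocol 5.4.2 lets the investigator and sponsor agree otherwise.
- The DLT experience points to a small effect from that trigger.
- RP2D choice rests on the primary and secondary endpoints (Protocol 3.6). Discontinuation is not a listed endpoint, and SAP 5.1.1 plans no hypothesis testing.
- TEAEs overall, Grade ≥3 TEAEs, SAEs and DLTs by treatment group do not depend on the reduction rule. Adverse-event listings allow case-by-case reading, so it would be wrong to say that the output cannot be reconciled.
- The SAP groups are defined by dose, so they are not limited to the randomised patients.
- A dose below 90% of plan, such as an incomplete infusion, can still count as a reduction at 0.24 mg/kg.

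All of this limits the size and certainty of the effect, but it does not remove the directional bias. The Grade ≥3 tables do not capture recurrent Grade 2 toxicity, the DLT criteria are built on Grade 3 and 4 events, and SAE tables capture it only when it is serious. The DLT window is two cycles, while treatment may last 2 years.

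**Conclusion.** The concern holds as a directional bias in a descriptive table. Relative to 0.6 and 1.2 mg/kg, the discontinuation tables overstate intolerance at 0.24 mg/kg, and the dose-reduction table leans the other way. With equal true toxicity the excess at 0.24 mg/kg is q(1 − s) over 0.6 mg/kg and q(1 − s²) over 1.2 mg/kg. That is about 1.5 to 1.9 percentage points for q = 2% and 7.5 to 9.4 points for q = 10%, both at s = 25%.

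These sizes rest on assumed q and s, on equal toxicity across doses, and on the reduction rule being followed. The documents fix neither q nor s. The effect may be small, and the final ranking of doses is not determined by the rule.

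**What to change.** In SAP 6.6.1.1 and 6.6.1.2, add TEAEs and related TEAEs leading to PF-05082566 dose reduction or permanent discontinuation, by treatment group, counting each patient once. Derive them from the action-taken field on the adverse-event eCRF page, and present them alongside the discontinuation table. Footnote the discontinuation and dose-reduction tables to say that no lower dose level was available at 0.24 mg/kg in the expansion cohorts.

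The cost is one extra table (all and related events) and two footnotes in the SAP. No change to the dosing rule is proposed. That the field records dose reduction is an assumption to confirm against the eCRF. The combined count also still depends on the investigator's judgement that a reduction was required. In an open-label study, knowing that no lower level exists may influence that judgement, so the new table supplements the others and does not replace them.

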6.6.2. Deaths

The frequency (number and percentage) of patients in the safety analysis set who died and who died within 30 days and within 60 days after last dose of study treatment as well as the primary reason for death, will be tabulated based on information from the ‘Notice of Death’ and ‘Survival Follow-Up’ eCRFs, by treatment group.

- All deaths;
- Deaths within 30 days after last dose of study treatment;
- Deaths within 60 days after last dose of study treatment;
- Reason for Death:
 - Disease under study;
 - Study treatment toxicity;
 - Unknown;
 - Other.

In addition, date and cause of death will be provided in individual patient data listing together with selected dosing information (study treatment received, date of first / last administration, dose) and will include the following information:

- AEs with fatal outcome (list preferred terms of AEs with outcome=Fatal, as well as AEs of Grade 5);
- Flags for death ≤ 30 days and 31-60 days after last dose of study treatment.

6.6.3. Serious Adverse Events

The frequency (number and percentage) of patients with each of the following will be presented for treatment-emergent SAEs by treatment group:

- SAEs by SOC and PT;
- Related SAEs by SOC and PT.

The listings of all SAEs will also be provided with the relevant information with a flag for SAEs with onset outside of the on-treatment period.

6.6.4. Laboratory Data

6.6.4.1. Hematology and Chemistry Parameters

Laboratory results will be classified according to the NCI-CTCAE criteria version 4.03. Non-numerical qualifiers (with the exception of fasting flags) will not be taken into consideration in the derivation of CTCAE criteria (eg, hypokalemia Grade 1 and Grade 2 are only distinguished by a non-numerical qualifier and therefore Grade 2 will not be derived). Additional laboratory results that are not part of NCI-CTCAE will be presented according to the categories: below normal limit, within normal limits and above normal limit (according to the laboratory normal ranges).

Quantitative data will be summarized using simple descriptive statistics (mean, SD, median, Q1, Q3, minimum, and maximum) of actual values and changes from baseline for each nominal visit over time (unscheduled measurements would therefore not be included in these summaries as described in [Section 5.2.7](#)). End of Treatment visit laboratory results will be summarized separately. The changes computed will be the differences from baseline. Qualitative data based on reference ranges will be described according to the categories (ie, Low, Normal, High).

Abnormalities classified according to NCI-CTCAE toxicity grading version 4.03 will be described using the worst grade. For those parameters which are graded with two toxicities such as potassium (hypokalemia/hyperkalemia), the toxicities will be summarized separately. Low direction toxicity (eg, hypokalemia) grades at baseline and post baseline will be set to 0 when the variables are derived for summarizing high direction toxicity (eg, hyperkalemia), and vice versa.

For **WBC differential counts** (total neutrophil [including bands], lymphocyte, monocyte, eosinophil, and basophil counts), the absolute value will be used when reported. When only percentages are available (this is mainly important for neutrophils and lymphocytes, because the CTCAE grading is based on the absolute counts), the absolute value is derived as follows:

$$\text{Derived differential absolute count} = (\text{WBC count}) * (\text{Differential \%value} / 100)$$

If the range for the differential absolute count is not available (only range for value in % is available) then Grade 1 will be attributed to as follows:

- Lymphocyte count decreased:
 - derived absolute count does not meet Grade 2-4 criteria, and
 - % value < % LLN value, and
 - derived absolute count $\geq 800/\text{mm}^3$.
- Neutrophil count decreased:
 - derived absolute count does not meet Grade 2-4 criteria, and

- % value < % LLN value, and
- derived absolute count $\geq 1500/\text{mm}^3$

For **calcium**, CTCAE grading is based on Corrected Calcium and Ionized Calcium (CALCIO). Corrected Calcium is calculated from Albumin and Calcium as follows:

Corrected calcium (mmol/L) = measured total Calcium (mmol/L) + 0.02 (40 - serum albumin [g/L])

Liver function tests: Alanine aminotransferase (ALT), aspartate aminotransferase (AST), and total bilirubin (TBILI) are used to assess possible drug induced liver toxicity. The ratios of test result over upper limit of normal (ULN) will be calculated and classified for these three parameters during the on-treatment period.

Summary of liver function tests will include the following categories. The number and percentage of patients with each of the following during the on-treatment period will be summarized by treatment group:

- ALT $\geq 3 \times \text{ULN}$, ALT $\geq 5 \times \text{ULN}$, ALT $\geq 10 \times \text{ULN}$, ALT $\geq 20 \times \text{ULN}$;
- AST $\geq 3 \times \text{ULN}$, AST $\geq 5 \times \text{ULN}$, AST $\geq 10 \times \text{ULN}$, AST $\geq 20 \times \text{ULN}$;
- (ALT or AST) $\geq 3 \times \text{ULN}$, (ALT or AST) $\geq 5 \times \text{ULN}$, (ALT or AST) $\geq 10 \times \text{ULN}$, (ALT or AST) $\geq 20 \times \text{ULN}$;
- TBILI $\geq 2 \times \text{ULN}$;
- Concurrent ALT $\geq 3 \times \text{ULN}$ and TBILI $\geq 2 \times \text{ULN}$;
- Concurrent AST $\geq 3 \times \text{ULN}$ and TBILI $\geq 2 \times \text{ULN}$;
- Concurrent (ALT or AST) $\geq 3 \times \text{ULN}$ and TBILI $\geq 2 \times \text{ULN}$;
- Concurrent (ALT or AST) $\geq 3 \times \text{ULN}$ and TBILI $\geq 2 \times \text{ULN}$ and ALP $> 2 \times \text{ULN}$;
- Concurrent (ALT or AST) $\geq 3 \times \text{ULN}$ and TBILI $\geq 2 \times \text{ULN}$ and (ALP $\leq 2 \times \text{ULN}$ or missing).

Concurrent measurements are those occurring on the same date.

Categories will be cumulative, ie, a patient with an elevation of AST $\geq 10 \times \text{ULN}$ will also appear in the categories $\geq 5 \times \text{ULN}$ and $\geq 3 \times \text{ULN}$. Liver function elevation and possible Hy's Law cases will be summarized using frequency counts and percentages.

An evaluation of Drug-Induced Serious Hepatotoxicity (eDISH) plot will also be created, with different symbols for different treatment groups, by graphically displaying.

- peak serum ALT(/ULN) vs peak total bilirubin (/ULN) including reference lines at ALT=3×ULN and total bilirubin =2×ULN.
- peak serum AST(/ULN) vs peak total bilirubin (/ULN) including reference lines at AST=3×ULN and total bilirubin =2×ULN.

In addition, a listing of all TBILI, ALT, AST and ALP values for patients with a post-baseline TBILI $\geq 2 \times$ ULN, ALT $\geq 3 \times$ ULN or AST $\geq 3 \times$ ULN will be provided.

Parameters with NCI-CTC grades available:

The laboratory toxicities will be tabulated using descriptive statistics (number of patients and percentages) during the on-treatment period. The denominator to calculate percentages for each laboratory parameter is the number of patients evaluable for CTCAE grading (ie, those patients for whom a Grade 0, 1, 2, 3 or 4 can be derived).

- The summary of laboratory parameters by CTCAE grade table will include number and percentage of patients with Grade 1, 2, 3, 4, Grade 3/4 and any grade (Grades 1-4), laboratory abnormalities during the on-treatment period.
- The shift table will summarize baseline CTCAE grade versus the worst on-treatment CTCAE grade. The highest CTCAE grade during the on-treatment period is considered as the worst grade for the summary.

The above analyses apply to hematology and chemistry evaluations which can be graded per CTCAE, ie:

- Hematology:

Hemoglobin (HB), Leukocytes (white blood cell decreased), Lymphocytes (lymphocyte count increased/decreased), Neutrophils / Absolute Neutrophils Count (ANC) (neutrophil count decreased), Platelet Count (PLT) (platelet count decreased), Coagulation (activated partial thromboplastin time (aPTT) and prothrombin time (INR)).

- Serum Chemistry:

Albumin (hypoalbuminemia), Alkaline Phosphatase (alkaline phosphatase increased), Alanine Aminotransferase (ALT) (ALT increased), Amylase (serum amylase increased), Aspartate Aminotransferase (AST) (AST increased), Total Bilirubin (blood bilirubin increased, Cholesterol (cholesterol high), Creatinine (creatinine increased), Creatine Kinase (CPK increased), Potassium (hypokalemia/ hyperkalemia), Sodium (hyponatremia/ hypernatremia), Magnesium (hypomagnesemia/hypermagnesemia), Calcium (hypocalcemia/ hypercalcemia), Glucose (hypoglycemia/hyperglycemia), Gamma Glutamyl Transferase (GGT) (GGT increased), Lipase (lipase increased), Phosphates (hypophosphatemia), Triglycerides (hypertriglyceridemia).

Parameters with NCI-CTC grades not available:

Hematology and chemistry evaluations which cannot be graded per CTCAE criteria will be summarized as frequency (number and percentage) of patients with:

- shifts from baseline normal to at least one result above normal during on-treatment period;
- shifts from baseline normal to at least one result below normal during on-treatment period.

In this study, these apply to the following parameters:

- Hematology: Absolute Monocytes, Absolute Eosinophils, Absolute Basophils;
- Serum Chemistry: Chloride, Total Urea, Uric Acid, Total Protein, C-Reactive Protein, Lactate Dehydrogenase (LDH).

